## **8.4 Statistical Analysis Plan**

A complete description of the statistical analyses and methods will be available in the Statistical Analysis Plan (SAP), which will be finalized prior to unblinding.

### **8.4.1 Analysis of Demographic and Baseline Characteristics**

Descriptive statistics (mean, standard deviation, median, minimum and maximum) for age, height, weight, BMI, and comorbidity score at enrollment will be calculated overall and by vaccine groups.

Distributions of subjects by sex, ethnic origin (race, ethnicity), and previous vaccination status will be summarized overall, and by vaccine group.

#### **8.4.1.1 Concomitant Medications**

Use of concomitant medication will be presented by treatment, age cohort, therapeutic area, and preferred drug name.

Concomitant medications are all medications taken during the study period, including those started before but ongoing at vaccination.

If a start date for a medication is partially or fully missing, and it is unclear as to whether the medication is prior or concomitant, it will be assumed that it is concomitant.

Medications will be coded using the WHO Drug dictionary.

## 8.4.2 Analysis of Primary Objective(s)

### 8.4.2.1 Analysis of Primary Efficacy Objective(s)

Not Applicable.

### 8.4.2.2 Analysis of Co-Primary Immunogenicity Objectives

The co-primary immunogenicity objectives are:

1. To demonstrate that vaccination with aQIV elicits an immune response that is not inferior to that of an aTIV containing the same virus strains as the US licensed adjuvanted influenza vaccine (Fluad, aTIV-1), and an aTIV containing the alternate B strain (aTIV-2) among adults  $\geq 65$  years of age
2. To assess the immunogenicity of aQIV in adults  $\geq 65$  years of age, based on CBER (Center for Biologics Evaluation and Research) criteria

#### 8.4.2.2.1 Statistical Hypotheses

*Noninferiority of aQIV to aTIV-1 and aTIV-2*

To demonstrate that vaccination with aQIV elicits an immune response that is not inferior to that of an aTIV containing the same virus strains as the US licensed adjuvanted influenza vaccine (Fluad, aTIV-1), and an aTIV containing the alternate B strain (aTIV-2) among adults  $\geq 65$  years of age. according to the FDA Guidance on seasonal inactivated influenza vaccines (*Guidance for Industry Clinical Data Needed to Support Licensure of Seasonal Inactivated Influenza Vaccines 2007*).

aQIV will be considered to be noninferior to aTIV if, for each of the four strains, the following statistical criteria are met:

- The upper bound of the two-sided 95% CI for the ratio of the GMTs does not exceed 1.5. The GMT ratio will be calculated by  $GMT_{aTIV} / GMT_{aQIV}$
- The upper bound of the two-sided 95% CI for the difference between the SCRs does not exceed 10%. The difference in SCR will be calculated by  $SCR_{aTIV} - SCR_{aQIV}$

In mathematical notation, the statistical hypotheses to be tested for the primary immunogenicity analysis correspond to:

$H_0: GMTr_i > 1.5$ , for any strain

$H_a: GMTr_i \leq 1.5$ , for all strain

and

$H_0: Di > 10$ , for any strain

$H_a: Di \leq 10$ , for all strain

where  $GMTri$  is any of the 4 strain-specific post immunogenicity dose GMT ratios namely,

- $GMT_{aTIV-1}/GMT_{aQIV}$  for B/Yamagata strain
- $GMT_{aTIV-2}/GMT_{aQIV}$  for B/Victoria strain
- Pooled  $GMT_{(aTIV-1 \text{ and } aTIV-2)}/GMT_{aQIV}$  for A/H1N1 strain
- Pooled  $GMT_{(aTIV-1 \text{ and } aTIV-2)}/GMT_{aQIV}$  for A/H3N2 strain

and  $Di$  is the 4 strain-specific post dose SCRs ( $\pi_{aTIV-1}, \pi_{aTIV-2}, \pi_{aQIV}$ ) difference, namely,

- $\pi_{aTIV-1} - \pi_{aQIV}$  for B/Yamagata strain
- $\pi_{aTIV-2} - \pi_{aQIV}$  for B/Victoria strain
- Pooled  $\pi_{(aTIV-1 \text{ and } aTIV-2)} - \pi_{aQIV}$  for A/H1N1 strain
- Pooled  $\pi_{(aTIV-1 \text{ and } aTIV-2)} - \pi_{aQIV}$  for A/H3N2 strain

where  $\pi_v$  denotes the seroconversion rates for the  $v$ th vaccine (aQIV, aTIV-1, aTIV-2).

### *CBER Immunogenicity Criteria*

The endpoints of percent of subjects achieving seroconversion and HI titer  $\geq 1:40$  at Day 22 will be assessed against the criteria described in CBER Guidance Clinical Data Needed to Support the Licensure of Seasonal Inactivated Influenza Vaccines ([FDA, 2007](#)):

- The lower bound of the two-sided exact 95% CI for the percentage of subjects achieving seroconversion for HI antibody should meet or exceed 30% and
- The lower bound of the two-sided exact 95% CI for the percentage of subjects achieving an HI antibody titer  $\geq 1:40$  should meet or exceed 60%

Assuming that  $Y_{jk} \sim B(1, \pi_k)$ ,  $Z_{jk} \sim B(1, \tau_k)$ ,  $j=1, \dots, n$ , identical and independent Bernoulli distributed random variables with  $\pi_k$  representing the unknown SC proportion postvaccination and  $\tau_k$  representing the unknown SP (seroprotection, titer  $\geq 1:40$ ) proportion postvaccination in aQIV for strain  $k$ , where  $k$  denotes the 4 strains contained in aQIV vaccines, CBER requirements for the aQIV vaccine group translate into following hypothesis

$$H_{0k}^{(SC)}: \pi_k \leq 0.3 \quad \text{vs} \quad H_{1k}^{(SC)}: \pi_k > 0.3$$

$$H_{0k}^{(SP)}: \tau_k \leq 0.6 \quad \text{vs} \quad H_{1k}^{(SP)}: \tau_k > 0.6$$

All hypotheses related to CBER criteria will be tested on unadjusted 5% significance levels.

#### 8.4.2.2.2 Analysis Sets

The Per Protocol Set will be used for the primary immunogenicity analysis and a supporting analysis will be performed using the Evaluable Set, as noted in [Section 8.3.4. Evaluable Set – Immunogenicity Analysis](#). Duplicate tables of primary and secondary immunogenicity analyses may also be produced based on the Evaluable population if there is >1% difference in the total number of subjects between the Per-Protocol Population and the Evaluable Population.

#### 8.4.2.2.3 Statistical Methods

All statistical analyses for HI titers will be performed on the logarithmically transformed (base 10) values. Individual HI titers below the detection limit (<10) will be set to half of that limit (5).

Co-primary immunogenicity endpoints of GMT and SCR for each virus strain contained in the vaccine will be assessed for subjects  $\geq 65$  years overall. For A/H1N1 and A/H3N2 strains the two aTIV groups will be pooled.

Primary analysis will be performed for subjects  $\geq 65$  years for the Per-Protocol Set. The difference in SCRs will be presented with exact 95% (CIs). Each of the four strains will be analyzed separately.

For immunogenicity data, it may be reasonable to consider missing immunogenicity values as missing completely at random (MCAR), i.e. not informative. Therefore, the immunogenicity analysis will comprise a complete case analysis only, without introducing any bias. Imputation methods will not be used.

To determine the GMT ratio (adjusted analysis) a general linear model (GLM) will be fitted on log transformed (base ten) post-vaccination HI titer as the outcome variable and terms for covariates: vaccine treatment, pre-vaccination HI titer, age stratum, gender, vaccination history, age-by-vaccine interaction and study site. Potential covariate interaction effects will also be examined in the fit of the GLM. From the model, an adjusted difference in least square means (on the log scale) will be produced with 95% confidence limits. The estimated difference and the confidence limits will be back transformed to obtain an *adjusted GMT ratio* with 95% confidence limits. Each of the four strains will be analyzed separately. The adjusted GMT ratio will be the result for which the non-inferiority assessment of the HI GMT co-primary endpoint will be based on.

The statistical models might be reduced in case they fail to converge. Further details will be provided in the Statistical Analysis Plan.

The complete set of covariates that may be used in the model to calculate the adjusted GMT ratio will include treatment group (3 treatments), age sub-group (3 categories, ( $\geq 65$ -74,  $\geq 75$ -84, and  $\geq 85$  years), sex (male or female), influenza vaccination received prior year (Y or N), prevaccination mean GMT titer (value) and investigator site (site identifier)

The GLM specification is: Adjusted Analysis GMT Model: Log-transformed Post-vaccination HI Titer = Vaccine + Age Strata + Gender + Vaccination History [y/n] + Log-transformed Prevaccination HI Titer + Site + Age Strata\*Vaccine.

For any strain, the interaction term *Age Strata\*Vaccine* will be removed from the fit of the model if it is assessed to be not significant.

The measure of the *unadjusted* GMT ratio based on post-vaccination GMTs only will also be presented.

In line with the FDA Guidance on seasonal inactivated influenza vaccines (*Guidance for Industry Clinical Data Needed to Support Licensure of Seasonal Inactivated Influenza Vaccines 2007*). aQIV will be considered to be noninferior to aTIV if, for each of the four strains, the following statistical criteria are met:

- The upper bound of the two-sided 95% Confidence Interval (CI) for the ratio of the GMTs does not exceed 1.5. The GMT ratio will be calculated by  $\text{GMT}_{\text{aTIV}} / \text{GMT}_{\text{aQIV}}$
- The upper bound of the two-sided 95% CI for the difference between the SCRs does not exceed 10%. The difference in SCR will be calculated by  $\pi_{\text{aTIV}} - \pi_{\text{aQIV}}$

To achieve the CBER criteria:

- The lower bound of the two-sided 95% confidence interval for the percentage of subjects achieving seroconversion for HI antibody should meet or exceed 30%
- The lower bound of the two-sided 95% confidence interval for the percentage of subjects achieving an HI antibody titer  $\geq 40$  should meet or exceed 60%

Binary data (ie, percentages of subjects with seroconversion and with titer  $\geq 1:40$ ) will be summarized for each group using unadjusted estimates and will be reported together with two-sided exact 95% CIs. No multiplicity adjustment to the CI levels will be implemented.

*Handling of missing values for Immunogenicity Data:*

For immunogenicity data, it may be reasonable to consider missing immunogenicity values as missing completely at random (MCAR), ie, not informative. Therefore, the key secondary analysis will comprise a complete case analysis only, without introducing any bias. Imputation methods will not be used. Further details of the statistical methods will be provided in the SAP.

### **8.4.3 Analysis of Secondary Objective(s)**

#### **8.4.3.1 Analysis of Secondary Safety Objective(s)**

Not applicable.

#### **8.4.3.2 Analysis of Secondary Efficacy Objective(s)**

Not applicable.

#### **8.4.3.3 Analysis of Secondary Immunogenicity Objective(s)**

*Characterization of immunogenicity of aQIV, aTIV-1 and aTIV-2:*

The measures of immunogenicity of aQIV, aTIV-1 and aTIV-2 will be assessed in terms of HI antibodies. Serum HI antibody titers against the 4 influenza vaccine strains will be used to calculate:

- GMT: Geometric mean of HI titers on Day 1 and Day 22
- GMR: The geometric mean of the fold increase of post- vaccination HI titer over the pre-vaccination HI titer (Day 22/Day 1)
- The percentage of subjects with a titer  $\geq 1:40$  at Day 1 and Day 22
- SCR: the percentage of subjects with either a prevaccination HI titer  $< 1:10$  and a postvaccination HI titer  $\geq 1:40$  or a prevaccination titer  $\geq 1:10$  and a  $\geq 4$ -fold increase in postvaccination titer on Day 22

*Superiority of immunologic response for aQIV vs aTIV:*

Superiority of aQIV over aTIV-1 and aTIV-2 for antibody response to the alternate B strain will be assessed using the GMT ratio ( $GMT_{aTIV}/GMT_{aQIV}$ ) and difference in SCR

$(SCR_{aTIV} - SCR_{aQIV})$  at Day 22. Point estimates and 95% confidence limits will be obtained as described for the primary endpoint. Superiority will be declared if the upper limit of the two-sided 95% CI for the difference in  $SCR_{aTIV} - SCR_{aQIV}$  is  $< 0$  and the upper limit of the two-sided 95% CI for the GMT ratio ( $GMT_{aTIV}/GMT_{aQIV}$ ) is  $< 1$  for both B strains.

#### 8.4.3.3.1 Statistical Hypotheses

No statistical testing will be performed for the first secondary immunogenicity objectives.

*Superiority of B-strain response (geometric mean titers and proportions of subjects with seroconversion):*

For superiority of aQIV B strain response, the hypotheses are that immunologically aQIV is superior compared to aTIV-1 and aTIV-2 for the B strain that is not included in each TIV vaccine separately. In mathematical form, these are:

$$H_{0k}^{(GMT)}: GMTr_k \geq 1 \text{ vs } H_{1k}^{(GMT)} GMTr_k < 1 \text{ for } k=1,2$$

and

$$H_{0k}^{(SCR)}: D_k \geq 0 \text{ vs } H_{1k}^{(SCR)} D_k < 0 \text{ for } k=1,2$$

where  $GMTr_k$  is the ratio of geometric mean titer  $GMT_{aTIV-k}/GMT_{aQIV}$  of mismatched B strain for  $k=1, 2$ , and  $D_k$  is the differences  $\pi_{aTIV-k} - \pi_{aQIV}$  of mismatched B strain Day 22 SCR differences for  $k=1,2$ .

#### 8.4.3.3.2 Analysis Sets

The secondary objective superiority testing will be performed using the Per Protocol Set (PPS).

#### 8.4.3.3.3 Statistical Methods

All statistical analyses for HI titers will be performed on the logarithmically transformed (base 10) values. Individual HI titers below detection limit ( $<10$ ) will be set to half of that limit (5).

Unadjusted for GMTs, GMRs and pertaining two-sided 95% CIs will be calculated assuming log-normal distribution of the titers and will be completed by providing minimum, maximum and median titers for each vaccine group.

Binary data (ie, percentages of subjects with seroconversion and with titer  $\geq 1:40$ ) will be summarized for each group using crude estimates and will be reported together with 2-sided exact 95% CIs. No multiplicity adjustment to the CI levels will be implemented.

For immunogenicity data, it may be reasonable to consider missing immunogenicity values as missing completely at random (MCAR), ie, not informative. Therefore, the key secondary analysis will comprise a complete case analysis only, without introducing any bias. Imputation methods will not be used.

Further details of the statistical methods will be provided in the SAP.

#### **8.4.4 Secondary Safety Objective**

##### **8.4.4.1 Analysis of Extent of Exposure**

The number and percentage of subjects actually receiving the vaccination will be summarized by vaccine group.

##### **8.4.4.2 Analysis of Solicited Local, Systemic and Other Adverse Events**

Solicited local AEs include: injection site erythema, induration, ecchymosis and pain.

Solicited systemic AEs include: loss of appetite, nausea, fatigue, generalized myalgia, generalized arthralgia, headache, chills, vomiting, diarrhea.

All solicited adverse events will be summarized according to defined severity grading scales.

Frequencies and percentages of subjects experiencing each adverse event will be presented for each symptom severity. Summary tables showing the occurrence of any local or systemic adverse event overall and at each time point will also be presented.

Postvaccination solicited adverse events reported from Day 1 to Day 7 will be summarized for the intervals Day 1-3, Day 4-7, Day 1-7 by maximal severity and by vaccine group, excluding the 30-minute measurement, which will be summarized separately. Injection-site erythema, ecchymosis and induration will be summarized according to categories based on linear measurements. Please refer to the SAP for definitions of categories.

Injection site pain and systemic adverse events (except fever) occurring up to 7 days after each vaccination will be summarized according to “mild”, “moderate” or “severe” categories. For the definition of severity grades please refer to [Section 7.1.1, Solicited Adverse Events](#) of the protocol.

Each solicited local and systemic adverse event will also be further summarized as “none” versus “any”. “Any” will include measurements with a diameter of at least 1 mm.

Implausible measurements (for further definition see SAP) will be left out of the analysis.

Use of antipyretics and analgesics will be summarized by frequency and percentage of subjects reporting use. Summaries by type of use (prophylactic versus treatment) and by vaccine group will be provided. The influence of antipyretics and analgesics use on the occurrence of specific adverse events (e.g., fever, pain) may be assessed.

Body temperature will be summarized by 0.5 °C and 1.0 °C increments from 36.0 °C up to  $\geq 40$  °C and will be broken down according by route of measurement. In addition, fever will be summarized according to “mild”, “moderate” or “severe” categorization. For the definition of severity grades please refer to the SAP.

#### **8.4.4.3 Analysis of Unsolicited Adverse Events**

This analysis applies to all adverse events occurring during the study, judged either as probably related, possibly related, or not related to vaccination by the Investigator, recorded in AE CRF, with a start date on or after the date of first vaccination. AE starting prior to the first vaccination will only be listed. The original verbatim terms used by investigators to identify adverse events in the CRFs will be mapped to preferred terms using the MedDRA dictionary. The adverse events will then be grouped by MedDRA preferred terms into frequency tables according to system organ class.

All reported adverse events, as well as adverse events judged by the investigator as at least possibly related to study vaccine, will be summarized according to system organ class and preferred term within system organ class (SOC). These summaries will be presented by vaccination group and by interval of study observation. When an adverse event occurs more than once for a subject, the maximal severity and strongest relationship to the vaccine group will be counted.

Separate summaries will be produced for the following categories:

- Serious adverse events
- Adverse events that are possibly or probably related to vaccine
- Adverse events of special interest
- New onset of chronic disease
- Adverse events leading to withdrawal
- Adverse events resulting in death

Data listings of all adverse events will be provided by subject. In addition, adverse events in the categories above will be provided as listed data.

For handling of missing data, the entire study period will be divided into disjoint intervals based upon the time and event schedule in the protocol:

Solicited AEs: 30 min, 6h-Day 3, Day 4-Day 7, and one overall interval: 6h-Day 7.

Unsolicited AEs: [Day 1-22], [Day 23-181], and [Day 1-181].

No imputation of missing solicited or unsolicited AEs will be used. The percentage of subjects with missing solicited AE assessments (eg, missing Diary Card) and missing Safety Phone Call or safety assessment will be reported for each time period.

#### **8.4.4.4 Analysis of Safety Laboratory Values**

Not applicable.

#### **8.4.5 Analysis of Exploratory Objectives**

The exploratory objectives are:

1. Additional optional objectives include characterization of the immunogenicity of aQIV using other immunological assays (e.g., virus neutralization [MN] or anti-neuraminidase antibody assays may be performed)
2. To explore the association between immune response after administration of aQIV or the aTIV-1, containing the same virus strains as the US-licensed adjuvanted trivalent influenza vaccine, or the aTIV-2 containing the alternate B strain by baseline characteristics.

##### ***Exploratory immunogenicity objective 1***

Exploratory objectives related to the MN-assay, immune response to heterologous influenza strains, or different antigens will be evaluated using similar methods for log normal, binomial data, and GMT and SCR as described in the statistical method for primary and secondary immunogenicity analysis.

##### ***Exploratory immunogenicity objective 2***

- GMTs: Geometric mean of HI titers prevaccination (Day 1) and at Study Exit Visit
- Percentage of subjects with four-fold rise

Analyses of the exploratory immunogenicity endpoints will be performed with adjustment for covariates including prevaccination titer, vaccination history, age and gender to evaluate the contribution of these factors to variations in the immune response. The covariate adjustment will be performed with all of the specified covariates in the general linear model.

The full model specification for the GMT titers will be:

*Log-transformed Post-Vaccination HI Titer = Vaccine + Age Strata + Gender + Vaccination History + Log-transformed Prevaccination HI Titer.*

The full model specification for the SCR rates will be:

*SCR = Vaccine + Age Strata + Gender + Vaccination History + Log-transformed Prevaccination HI titer*

Seroconversion rates will be analyzed using a logistic regression model, and GMT titers will be log transformed (base 10) and analyzed with a general linear model. Pre-vaccination titers will be log transformed and entered as a continuous covariate.

Vaccination history will be a categorical variable indicating whether or not an individual received an influenza vaccination in the previous year. If the proportion vaccinated in the previous year is close to 100% then this covariate may be omitted to avoid creating an unstable model. Age will be entered according to the predefined strata ( $\geq 65-74$ ,  $\geq 75-84$ , and  $\geq 85$  years). For the logistic regressions, the odds ratios will be presented with 95% CIs for each effect in the model. For the GLM least square mean estimates for the GMT ratio will be presented with 95% confidence limits for each effect in the model.

Further details of the analysis of exploratory be provided in the SAP.

## 8.5 Sample Size and Power Considerations

aQIV will be tested against aTIV comparators. The treatment randomization ratio is 2:1:1 (aQIV: aTIV-1: aTIV-2). This study is powered to achieve 80% power to demonstrate noninferiority over 8 co-primary endpoints, seroconversion rates for 4 strains, GMT for 4 strains using a one-sided alpha of 0.025 for each comparison. No adjustment for multiple endpoints will be made.

For comparisons of SCR a noninferiority margin of 10% (aTIV – aQIV) will be employed. It is assumed that the SCRs for A/ H1N1, A/ H3N2 and B strains for TIV are 73%, 73% and 40% respectively. These estimates are based on the estimated SCR rates of historical data, namely study protocol V70\_27. It has been assumed that there is no difference in terms of SCR between aQIV and aTIV for all strains. For comparison of the GMT ratio, a noninferiority of 1.5 (aTIV/aQIV) will be employed. It is assumed that there is no difference between aQIV and aTIV (i.e., a ratio of 1) and that the standard deviation of log (titer) is 1.2.

Under these assumptions, N evaluable = 800 in the aQIV group and 400 in each aTIV group providing 800 and 800 subjects receiving aQIV and aTIV respectively for comparisons of A strains, and 800 and 400 subjects receiving aQIV and aTIV respectively for comparisons of B strains. This provides a total N evaluable = 1600. These numbers provide 99.45% power to detect differences in SCR for each A strain and 91.29% power for each B strain, providing overall 82.42% power for the 4 SCR tests.

For GMT ratio tests each A strain test will have 100% power and each B strain test will have 99.98% power, providing 99.96% power for the 4 GMT ratio tests and consequently 82.39% power for the 8 co-primary endpoints. Overall 1600 evaluable subjects will be required. Allowing for a 10% drop-out N=1778 subjects will be recruited (Sample size calculations were performed using PASS v12).

The immunogenicity was powered to meet the criteria prespecified in the CBER guidance for acceptable immunogenicity: namely,

- the lower bound of the two-sided 95% confidence interval for the percent of subjects achieving seroconversion should exceed 30%, and
- the lower bound of the two-sided 95% confidence interval for the percent of subject achieving HI antibody titer  $\geq 40$  should exceed 60%

With a sample size of N=800 (evaluable) subjects for the aQIV group if the population SCR for A/ H1N1, A/ H3N2 and B strains for TIV is 73%, 73% and 40% respectively then the probability of observing a seroconversion rate that is significantly greater than 30% is approximately 100% (for the A/H1N1), 100% for A/H3N2 and 100% (for the B-strains).

With a sample size of N=800 (evaluable) subjects for the aQIV group if the population SP rates for A/ H1N1, A/ H3N2 and B strains for TIV is 91%, 99% and 64.6% respectively (as observed in V70\_27) then the probability of observing a SP rate that is significantly greater than 60% is approximately 100% (for the A/H1N1), 100% for A/H3N2 and 76.47% (for the B-strains).

**Table 8.5-1** summarizes the list of all co-primary endpoints with strains, the planned noninferiority margin and underlying assumptions used for the sample size computations.

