## 8. STATISTICAL CONSIDERATIONS

### 8.1 Endpoints

#### 8.1.1 Primary Endpoints

##### 8.1.1.1 Co-Primary Immunogenicity Endpoints

The immunogenicity of study vaccines will be assessed 21 (i.e., on Day 22) days after vaccine administration by measuring the hemagglutination inhibition (HI) antibody titers to the four virus strains included in the vaccines.

The noninferiority of aQIV compared to aTIV-1, and to aTIV-2 will be assessed for the eight co-primary endpoints of HI geometric mean titer (GMT) and seroconversion rate (SCR) for each virus strain included in the vaccines as follows:

- The GMT ratio\* for the A/H1N1 strain
- The GMT ratio for the A/H3N2 strain
- The GMT ratio for the B strain (Yamagata lineage)
- The GMT ratio for the B strain (Victoria lineage)
- The difference between the SCR\*\* for the A/H1N1 strain
- The difference between the SCR for the A/H3N2 strain
- The difference between the SCR for the B strain (Yamagata lineage)
- The difference between the SCR for the B strain (Victoria lineage)

Immunogenicity results obtained from aTIV-1 and aTIV-2 for both A/H1N1 and A/H3N2 strains will be pooled for comparison with aQIV.

*\*The GMT ratio is defined as the geometric mean of the post-vaccination (Day 22) HI titer for aTIV-1 (or aTIV-2) over the geometric mean of postvaccination (Day 22) HI titer for aQIV.*

*\*\*The SCR is defined as the percentage of subjects with either a prevaccination HI titer < 1:10 and a post-vaccination HI titer  $\geq$  1: 40 or a prevaccination HI titer  $\geq$  1:10 and a  $\geq$  4-fold increase in postvaccination HI titer.*

The second co-primary immunogenicity objective for aQIV will be assessed 21 days after vaccine administration by applying CBER criteria for the elderly population for each of the 4 strains included in aQIV:

- The percent of subjects achieving seroconversion for HI antibody

- The percent of subjects achieving an HI antibody titer  $\geq 1:40$

The study is considered successful if the (16) co-primary endpoints are achieved.

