2.1.2 CO-PRIMARY ENDPOINTS

The immunogenicity of study vaccines will be assessed 21 days (i.e., on Day 22) after vaccine administration by measuring the hemagglutination inhibition (HI) antibody titers to the virus strains included in the vaccines.

The non-inferiority of aQIV compared to aTIV-1, and to aTIV-2 will be assessed for the eight co-primary endpoints of HI geometric mean titer (GMT) and seroconversion rate (SCR) for each virus strain included in the vaccines as follows:

- The GMT ratio* for the A/H1N1 strain;
- The GMT ratio for the A/H3N2 strain;
- The GMT ratio for the B strain (Yamagata lineage);
- The GMT ratio for the B strain (Victoria lineage);
- The difference between the SCR** for the A/H1N1 strain;
- The difference between the SCR for the A/H3N2 strain;
- The difference between the SCR for the B strain (Yamagata lineage);
- The difference between the SCR for the B strain (Victoria lineage).

Immunogenicity results obtained from aTIV-1 and aTIV-2 for both A/H1N1 and A/H3N2 strains will be pooled for comparison with aQIV.

*The GMT ratio is defined as the geometric mean of the post-vaccination (Day 22) HI titer for aTIV-1 (or aTIV-2) over the geometric mean of post-vaccination (Day 22) HI titer for aQIV.

**The SCR is defined as the percentage of subjects with either a pre-vaccination HI titer $< 1:10$ and a post-vaccination HI titer $\geq 1:40$ or a pre-vaccination HI titer $\geq 1:10$ and a ≥ 4 -fold increase in post-vaccination HI titer.

The second co-primary immunogenicity objective for aQIV will be assessed 21 days after vaccine administration by applying CBER criteria for the elderly population for each of the 4 strains included in aQIV. The second co-primary endpoints include:

- The percent of subjects achieving seroconversion (SC) for HI antibody
- The percent of subjects achieving an HI antibody titer $\geq 1:40$

The study is considered successful if all co-primary endpoints are achieved.

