2.4 SUCCESS CRITERIA

The study is considered successful if both co-primary objectives are achieved.

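### The 80% power target covers 8 non-inferiority endpoints, but success needs all 16; on the plan's own figures, power for the success rule is at most 76.47%, and about 48% with both B strains counted under independence

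*Protocol*

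**What the plan says.** **Success rule.** Protocol 8.1.1.1: "The study is considered successful if the (16) co-primary endpoints are achieved". SAP 2.1.2: "The study is considered successful if all co-primary endpoints are achieved". SAP 2.4: "The study is considered successful if both co-primary objectives are achieved". Eight endpoints are non-inferiority tests (GMT ratio and SCR difference for each of four strains). The other eight are CBER criteria in the aQIV arm (seroconversion, and titer ≥1:40, for each of four strains). The synopsis adds that both CBER criteria must be met for every strain.

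**Power target.** Protocol 8.5: "This study is powered to achieve 80% power to demonstrate noninferiority over 8 co-primary endpoints". SAP 5 repeats the sentence. The text goes from the SCR powers to 82.42%, then to 82.39% with the GMT tests added, and then to the requirement for 1600 evaluable subjects.

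**CBER set.** After the sample size has been reached, both documents say that immunogenicity was powered for the CBER criteria. They give 76.47% for the B-strain titer ≥1:40 criterion. Protocol Table 8.5-1 and SAP Table 5-1 carry 76.47% into two further rows: global power for the four titer endpoints, and global power for the CBER set as a whole. No row or sentence gives the power for both sets together.

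**The concern.** The stated target and the declared success rule are not the same event. The rule needs every one of 16 tests to pass; the target concerns 8 of them. A conjunctive rule can be no more powerful than its weakest test, and the weakest one lies in the half left out of the target.

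There is a second, smaller fault in the tables. For SCR non-inferiority the two B strains are counted as two tests. For titer ≥1:40 the same two strains are counted as one.

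What is at stake is the planning figure that a sponsor, ethics committee or regulator would use for the chance that the study meets its success criterion when aQIV and aTIV do not differ. That figure is missing, and the ones printed around it are more favourable than it would be.

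**Working it through.** **Inputs** (Protocol 8.5 and Table 8.5-1; same values in SAP 5)
- Group sizes: "N evaluable = 800 in the aQIV group and 400 in each aTIV group", so 800 v 800 for A strains and 800 v 400 for each B strain.
- Level: "using a one-sided alpha of 0.025 for each comparison".
- SCR: margin 10 points; true rates 73%, 73% and 40%; no difference between arms.
- GMT ratio: margin 1.5; true ratio 1; SD of the natural-log titer 1.2.
- CBER thresholds: 30% (seroconversion) and 60% (titer ≥1:40). Assumed titer ≥1:40 rates: 91%, 99% and 64.6% (B strains).

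**Step 1. Reproduce the non-inferiority figures.**
- SCR, score test with null-constrained variance: 99.45% for each A strain and 91.29% for each B strain, as printed. The unpooled version for a B strain has SE = √(0.4 × 0.6 × (1/800 + 1/400)) = 0.030, and Φ(0.10/0.030 − 1.96) = 91.5%.
- Four SCR tests: 0.9945² × 0.9129² = 82.42%, as printed. Each B strain is counted.
- GMT, B strain: SE = 1.2 × √(1/800 + 1/400) = 0.0735, and Φ(ln 1.5/0.0735 − 1.96) = 99.98%. A strains exceed 99.99%. Four tests: 0.9998² = 99.96%.
- Eight tests: 0.8242 × 0.9996 = 82.39%, as printed. The plan's convention is thus to multiply as if the tests were independent.
- Enrolment: 1600/0.9 = 1778, as printed.

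**Step 2. Reproduce the CBER figures.**
- Seroconversion, 40% against 30%, n = 800: above 99.99%.
- Titer ≥1:40, one B strain, 64.6% against 60%, n = 800: score test 76.2%, Wald 77.7%, exact interval 75.5% (needs at least 508 of 800). The printed 76.47% is within this spread and is the power for one strain.

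**Step 3. CBER set with both B strains.** Under the convention of step 1: 0.7647² = 58.5%. The printed 76.47% would be right for two strains only if the two tests always passed or failed together. The documents assume no such thing.

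**Step 4. All 16 endpoints.**
- Ceiling under any dependence: the smallest component, 76.47%. Shortfall against 82.39%: 5.92 points.
- Printed block values multiplied: 0.8239 × 0.7647 = 63.0%. Shortfall: 19.4 points.
- Both B strains counted, independence: 0.8239 × 0.7647² = 48.2%. Shortfall: 34.2 points.

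**Step 5. Sensitivity to correlation.** The documents give no correlations, so they were assumed. B-strain seroconversion and titer indicators in the 800 aQIV subjects were simulated from correlated latent normals, 4000 trials per setting. CBER tests used the exact cut-offs and non-inferiority used the Wald interval. The A-strain SCR and GMT powers were applied as the fixed factor 0.9945² × 0.9996.

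| Correlation of SC with titer ≥1:40, within strain | Correlation between B strains | CBER set (B strains) | All 16 |
|---|---|---|---|
| 0 | 0 | 57.6% | 48.0% |
| 0.5 | 0.3 | 59.5% | 50.4% |
| 0.8 | 0.8 | 64.5% | 56.8% |
| 0.95 | 0.95 | 67.4% | 59.1% |

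Simulation error is about 0.8 points (√(0.5 × 0.5/4000)). A further set of runs, with correlations up to 0.7 within strain and 0.6 between strains, gave 46.7% to 52.3%. The overall range is about 47% to 59%.

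**The case against.** The strongest reply is that nothing is hidden. The 80% sentence names its own scope, non-inferiority over 8 endpoints, and 82.39% is correct for that scope. The CBER set is labelled in Table 8.5-1 as the second group of co-primary endpoints, and its 76.47% stands below the 82.39%. Anyone reading the whole table sees that a required set falls under 80%. This stands: a reader might infer that the plan ignored CBER power or miscalculated the non-inferiority power, and the documents support neither.

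A second reply is that the endpoints are positively correlated, because seroconversion and titer ≥1:40 come from the same sera and both B strains are measured in the same aQIV subjects. This also stands, and it is why 48.2% should not be read as the single true value. It does not rescue the target, because the 76.47% ceiling needs no assumption about correlation.

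A third reply is that a failure could hardly be misread, since results are judged by strain and by criterion. That is fair. A reader might infer that a failed study would be taken as evidence against aQIV, but a miss confined to B-strain titer ≥1:40 would be visible as such.

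What the replies leave unanswered is that two separate block powers do not give the power of a rule that needs both, and that one of the two counts a single B strain where there are two.

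**Conclusion.** Wrong as written, in two respects. The 80% target and the 1600 evaluable subjects are tied to half of the endpoints that the success rule requires. The two CBER global-power rows also print the one-strain figure for two B strains.

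Taking the plan's component powers as given, power for study success is at most 76.47% whatever the dependence. It is 63.0% if both printed blocks are multiplied, and 48.2% if both B strains are counted under the plan's multiplication. The range of about 47% to 59% rests on assumed correlations. The limiting item is the B-strain titer ≥1:40 criterion, assumed at 64.6% against a 60% threshold.

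A reader might go further and infer that the decision rule is invalid. The documents do not support that: requiring every test to pass does not inflate type I error, and the finding concerns only how the power is described. Nor does it show that the sample size has to change.

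**What to change.** Make the same changes in Protocol 8.5 and Table 8.5-1, the matching synopsis text, and SAP 5 and Table 5-1:

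1. Correct the two CBER global-power rows (the four titer ≥1:40 endpoints, and the CBER set) from 76.47% to about 58% (0.7647²; two B strains, independence), noting a maximum of 76.47% under any dependence. The per-strain 76.47% stays.
2. Add a row: *Global power for study success (all 16 co-primary endpoints): about 48% under independence, at most 76.47% under any dependence.*
3. Reword the opening sentence: *The study has 82.39% power for co-primary objective 1 (the 8 non-inferiority endpoints) alone. Power for the study success criterion is below 80%, limited by the B-strain titer ≥1:40 criterion.*

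Changes 1 and 2 belong together; a 48% row beneath an uncorrected 76.47% would not multiply through, since 0.8239 × 0.7647 is 63.0%. The sample size, the success rule and the procedures stay as they are. The only cost is a less favourable stated power.
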